**The Inter-relationship between Vitamin D: Bone, Illness,
Injury and its Impact on Exercise Performance**
(The D-Biicep Study)

Study personnel and contact details

Principal investigator:

[name]
Department of Nutritional Sciences
Faculty of Health & Medical Sciences,
University of Surrey, Stag Hill campus
[name]
[contact]
Email: [contact]

Co-investigators:

[name] (PhD student)
Department of Nutritional Sciences
Faculty of Health & Medical Sciences
University of Surrey, [name]
[contact]
Email: [contact]

[name]
Department of Nutritional Sciences
Faculty of Health & Medical Sciences
University of Surrey, Manor Park Campus
[name]
[contact]
Email: [contact]

[name]
Department of Nutritional Sciences
Faculty of Health & Medical Sciences
University of Surrey, Manor Park Campus
[name]
[contact]
Email: [contact]

Synopsis

Title	The Inter-relationship between Vitamin D: Bone, Illness, Injury and its Impact on Exercise Performance
Acronym	The D-BIICEP Study
Chief Investigator	[name]
Objectives	To explore the inter-relationship between vitamin D status, calcium homeostasis, bone health, injury, illness and sport performance in young active adults.
Study Configuration	Assessment of vitamin D status, muscular strength, endurance capacity, body composition and bone mineral density in healthy university level athletes before and after 20 week of competitive training and non-trained control subjects before and after 20 weeks.
Setting	The Clinical Investigative Units (CIU), Department of Nutritional Sciences, University of Surrey Surrey Human Performance Institute (SHPI), Surrey Sports Park, Guildford
Sample size estimate	Sample size calculation is based on detecting a mean difference in 25 (OH) D status (study primary endpoint) between indoor and outdoor athletes, considering the standard deviation (13.2 ng.mL) and effect size (0.48) reported previously (Halliday et al 2011). To give 80% power and a significance level P < 0.05 the study will be conducted with 18 participants in each arm. To allow for 15% dropout 63 participants will be recruited
Number of participants	63 subjects; 21 trained males, 21 trained females and 21 controls(male and female)
Eligibility criteria	Males or females aged 18-30 that regularly partakes in training/ competition for a sport competing in BUCs (≥ 4 hrs/ week) will be eligible to enroll in the trained group. The untrained control group must not exceed 150 min/wk of physical activity. All subjects need to be in good physical health and should have a BMI > 18 kg/m ² and able to provide written informed consent.
Description of interventions	Two test sessions in which Vitamin D concentration, muscular strength and power, aerobic capacity, bone mineral content and body composition will be assessed. This will be followed by 20 weeks of normal training and competition. After this 20wk period the same two test sessions will be repeated.
Duration of study	~24 weeks
Outcome measures	Vitamin D concentration (25(OH)D Status) Handgrip and knee extension isometric strength Aerobic endurance capacity (VO ₂ max) Body composition, including total and regional assessments of lean and fat mass. Bone mineral content of the Tibia.

	Whole body and hip/femur bone mineral density.
Statistical methods	Descriptive data (Vit D, Strength, $VO_{2\text{ max}}$, fat, lean and bone mass) will be expressed as the group mean ($\pm SD$) or as the median (inter-quartile range) if the data are non-parametric. Comparison of pre- and post-training periods will be made using ANOVA.

Study background information and rationale

It is known that poor vitamin D status is a very common problem in the UK, specifically within the athletic community (Owens et al., 2014). It is also known that a lack of vitamin D availability has potentially serious health implications, especially with respect to bone and muscle function (Holick et al., 2005).

The risk of vitamin D deficiency or insufficiency among athletes is thought to depend largely on geographical location and type of sport (indoor vs. outdoor) (Halliday et al., 2011) but there is limited data on young adults within the United Kingdom partaking in University Sport. In addition to this there has been little research focussing upon the relationship between sport performance and vitamin D status. In line with this, little is known of the effects of different sports on bone health between the sexes. Weight bearing exercises such as rugby and basketball evoke very different mechanical loading profiles on the bone compared to non-weight bearing exercises such as swimming and can therefore also play an instrumental role in bone health in these physically active populations. Previous research has also failed to provide definitive conclusions upon the effect of Vitamin D status on bone, illness, injury and sport performance within the UK as most research has been at lower latitude (Forney et al., 2014).

A control group will be included into this study to explore whether young adults are also at significant risk of Vitamin D insufficiency or deficiency. This is because there is limited data on this population group. Therefore, the results obtained from this study will provide vital information on UK university populations and their vitamin D status. This will help to inform the wider scientific community to determine future public health strategies and thus potentially positively impacting on the health of the young adult sporting population and sedentary controls for years to come.

Study objectives and hypothesis

Primary objective

To determine the effects of regular training and competition on the inter-relationship between vitamin D status, calcium homeostasis, bone health, injury, illness and sport performance in young active adults.

Secondary objective

- i) To measure bone mineral density and content in winter and spring, and its relationship with Vitamin D status and the incidence of injury in athletes.

- ii) To measure vitamin D status in winter and spring to determine its relationship with the incidence of illness and fitness outcomes.
- iii) To distinguish the effects of indoor/outdoor/mixed training and competition on vitamin D status.
- iv) To interpret the effects of high/medium/low impact sports on bone mass.
- v) To measure changes in health and skill related components of fitness (vertical jump, hand-grip strength, knee extensor muscular strength and aerobic fitness) throughout an academic sporting season.
- vi) To measure any incidence of injury and illness that occurs between winter and spring and its correlation with Vitamin D status, training and bone health.
- vii) To ascertain whether there are any differences in the research outcomes between trained and control subjects

Hypothesis

We propose that athletes will have a sub-optimal (<50 nmol/l) of 25 (OH) D status at baseline and a poor vitamin D status (lowered plasma 25(OH)D) during the spring as a result of lower daylight exposure during the winter period. In addition to this we assume that those who regularly compete and train indoors will have a lower Vitamin D status at baseline due to insufficient exposure to ultraviolet B radiation from the Sun.

Study design

The D-BIICEP Study is an observational study. Participants will be assessed at baseline in winter (September/October) and again at the end of the observational period in spring (March/April).

Outline of Study

- **Pre-screening:** screening questionnaire is administered to participant.
- **Session 1:** Consent forms to be signed. pQCT test and weight, height and body composition. Hip and femoral head DEXA scan. Jump height and maximal oxygen uptake ($VO_{2\text{ max}}$) test.
- **Session 2:** Plasma samples collected and muscular strength tests performed.

20 weeks of training/ competition for their respective University Sport Team or regular physical activity levels for the control subjects.

Participants are expected to complete their Illness and Injury Questionnaire

- **Session 3:** pQCT test, weight, height and body composition. Hip and femoral head DEXA Scan. Jump height and maximal oxygen uptake ($VO_{2\text{ max}}$) test.
- **Session 4:** Plasma samples collected and muscular strength tests performed

Trial Visit Activities

During this study the subjects will be asked to visit the labs on two occasions, at the beginning of the study for baseline measurements, and again on two occasions at the end of the study.

At both trial visits, participants will have the following outcomes assessed:

- Sport performance: Vertical jump height, muscular strength and aerobic fitness
- Peripheral Quantitative Computed Tomography (pQCT) scan of the bone mineral composition of the tibia.
- Total and %age lean and fat mass and total bone mineral density via Dual Energy X-ray Absorptiometry (DEXA).
- Hip and femoral head bone mineral density and content to assess fracture risk via DEXA.
- Serum 25(OH)D levels, lipid profile, glucose, insulin, serum calcium, albumin, parathyroid hormone, C-terminal telopeptide (CTX), full blood count, kidney, thyroid and liver function ($\approx 15\text{ml}$ of whole blood will be collected for these measurements).
- Dietary intake using self-reported food diaries
- Illness and injury incidence will be recorded daily throughout the study in a booklet provided to the participants.

Aerobic fitness will be tested using a VO_2 max exercise protocol using a stationary cycle ergometer, the participants will be expected to perform this to maximal effort or exhaustion. The test will consist of progressive increments in cycling workload (power output, W) until volitional fatigue. The test will take about 8 – 12 minutes to complete and is dependent upon the fitness of the participants. This will take place in the Sport & Exercise Science laboratories based in the Clinical Investigation Unit (22AX00). All subjects will be supervised during exercise at all times and will implement an adequate warm-up and cool-down to minimize the risk of injury. Staff will be on hand throughout the testing trained adequately in basic life support (including defibrillation).

Muscular strength assessments will be performed at the Surrey Human Performance Institute. Muscular strength of the knee extensor and handgrip muscles will be determined using an Isokinetic Dynamometer and a handgrip dynamometer respectively. For each assessment three maximal effort isometric contractions will be performed and peak torque (nM) and strength (kg) will be recorded. Muscular power will be assessed through performance of a countermovement jump (CMJ).

Body composition (absolute and relative amount of lean and fat mass), whole body bone mineral density and hip and femur bone mineral density will be measured with the use of DEXA (located in the Sport & Exercise Science laboratories based in the Clinical Investigation Unit). Two scans will be performed: one for the assessment of whole body bone mineral density and body composition, and the other scan is performed to specifically assess fracture risk by scanning the hip and femoral head. Effective exposure doses for these scans are $\sim 8\mu\text{Sv}$ and $\sim 4\mu\text{Sv}$ respectively. The total effective dose is depending on the size ('thickness' & height) of the volunteer and is approximately equivalent to the cosmic radiation exposure received in 45min of a transatlantic flight, or the radiation dose received on eating 80g of brazil nuts (Health Protection Agency).

Bone mineral content of the tibia will be assessed using pQCT and this will be correlated to bone mineral density data obtained from DEXA. One scan will be performed and effective exposure doses will be between 1.5-1.8 μ Sv which is comparable to 10min on a transatlantic flight or one handful of brazil nuts. The estimated total exposure dose for a single subject during the entire study is ~28 μ Sv which is the same level of exposure as an average UK citizen is exposed to over the course of 4 days via background radiation.

Results of the body composition, bone mineral density, jump height, muscular strength, aerobic fitness (maximal oxygen uptake: VO₂max) and dietary intake from the self-reported food diaries will be made available to the subjects upon request. The results from the blood analysis will be reported to the subject if there are any health concerns raised. If the results are within healthy ranges the participants will not be contacted unless they specifically request for this information. The investigators will not be contacting their GPs if there are any concerns raised in the study however we will stress that they should contact their GP themselves to discuss the results we found.

Upon commencing the study, the participants will be required to track their incidence of illness and training habits during the 20-week experimental period between baseline and conclusion measurements. Throughout this period they must record the incidence of illness and days trained during the months in a check-list booklet, which will be provided to them. An email reminder will be sent to prompt all participants to complete these booklets on a daily basis during the experimental period, this should only take 1-2 minutes every evening. Throughout the duration of the trial, the participants will be contacted via telephone/ email on a monthly basis to discuss any issues and maintain good communication.

Recruitment

Participants will be recruited from the University of Surrey; posters will be positioned around the Stag Hill campus, Manor Park Campus and Hazel Farm. Flyers will be placed in communal areas, the students' union, the university library and at Surrey Sports Park to promote awareness for the study. In addition to this, a brief presentation will be given to students following their lectures in the same format as the poster or flyer.

Coaching staff and the signatories of Team Surrey committees will also be approached for the study and flyers will be provided to hand out to their team members if they are keen to complete this as a team. Social media sites such as Facebook will be used to publicise the study: the poster or flyer will be inserted as a photo with permission of the administrator of the Facebook pages.

If the individual is interested in participating in the study after reading the information sheet, they will contact the investigator and session 1 will be arranged. A member of the research team will inform the participant of all aspects pertaining to participation in the study before consent is sought.

Children, and other vulnerable groups, including those unable to provide informed consent will not be recruited. Moreover, we do not have access to translator or interpreter services, so will not recruit those who do not have a good understanding of the English language either in written or oral form.

It will be explained to the potential participant that entry into the study is entirely voluntary and that they can withdraw at any time. In the event of their withdrawal it will be explained

that their data collected so far could be erased, but we will seek their consent to use the data collected up to the point of withdrawal in the final analyses where appropriate.

University Athlete Inclusion criteria

- Male or female
- Aged 18-30
- Regularly train/compete for Team Surrey Basketball, Boat Club, Swimming and Waterpolo, Netball or Rugby (for more than 4 hours/week)
- In good physical health
- Have a BMI >18 kg/m²
- Able to provide written informed consent

Control Group Inclusion Criteria:

- Male or Female
- Age 18-30
- Do **not** use sun beds/ will not be going on a sun holiday/ returning home to a traditional sun holiday location between February 2017 and October 2017. This is because the results will be used to represent the Vitamin D status of young sporting individuals residing within the UK during these seasons.
- Do **not** take supplements containing Vitamin D
- Do **not** compete for Team Surrey and exercise less than 150 minutes / week.
- BMI: 18 – 30 kg/m²

Exclusion criteria

- Currently receiving treatment for medical conditions that are likely to affect vitamin D metabolism
- Hypercalcaemia (>2.5mmol/L)
- Regular use of sun-beds
- Having a sun holiday one month prior to commencing the study or plans for a sun holiday within the study period or will be returning home to a sun holiday location.
- Use of vitamin supplements containing vitamin D (if the prospective participants agrees to stop Vitamin D supplementation to join the study, a wash-out period of 8 weeks prior to commencing the trial would be acceptable).
- Excess alcohol intake for participants aged 18 years (> 21 units for males, > 14 units for females per week, as per Government guidelines)
- Those under dietary restriction (except vegetarianism) or following a weight-reducing diet.
- Clinically significant haematological abnormalities other than mild anaemia (Hb <12.0g/dl)
- Active malignancy
- Pregnant or planning a pregnancy during the study period

If a participant is subsequently found to be ineligible for the study their screening questionnaire will be destroyed due to the questionnaire containing sensitive information.

Participant Withdrawal

All participants will be notified during the consenting process that they are free to withdraw from the trial at any time, without giving a reason.

Participants will be withdrawn from the trial by the Principal Investigator if:

1. The participant develops a medical condition or becomes pregnant either prior to entering the study or during, which may adversely affect the outcome of the study.
2. It is clearly demonstrated that the participant is non-compliant completing study activities and the control procedures requested of them.
3. If the participant suffers an serious adverse event

All data prior to subject withdrawal will be used in analysis; unless the participant specifically requests that their data is not to be used. Withdrawn participants will not be replaced as an anticipated drop-out rate of 15% has been accounted for in the recruitment targets.

Informed consent

All participants will provide written informed consent for participation, and use and retention of the study data. The Consent Form will be signed and dated by the participant before they enter the study. The Investigator will explain the details of the study and provide a Participant Information Sheet and a DEXA information folder, ensuring that the participant has sufficient time to consider participating or not. The Investigator will answer any questions that the participant has concerning study participation.

Informed consent will be collected from each participant before they undergo any interventions (including physical examination and history taking) related to the study. One copy of this will be kept by the participant and one will be kept by the Investigator.

Those incapable of providing valid consent will not be recruited. Participants under the age of 18 will not be recruited.

Statistics, Sample size and justification

Statistical analysis based on preliminary data from our group and Halliday et al (2011) indicates that a minimum of 52 subjects is required in order to detect a 35% difference in vitamin D concentrations across seasons at a power of 80%, significance level $P<0.05$.

In order to achieve an equal division between genders, 26 males and 26 females from different indoor and outdoor sports across Team Surrey need to be recruited. Based on our preliminary study we are expecting a 15% drop out. We will therefore aim to recruit 63 subjects (21 females, 21 males and 21 sedentary controls, males and females).

Descriptive data ((25(OH)D status, jump height, muscular power, muscular strength, $VO_{2\ max}$, fat, lean and bone mass) will be expressed as the group mean ($\pm SD$) or as the median (inter-quartile range) if the data are non-parametric. Comparison of pre- and post-training periods will be made using ANOVA.

Quality assurance & audit

Insurance and indemnity

The University of Surrey has taken out an insurance policy to provide indemnity in the event of a successful litigious claim for proven non-negligent harm.

Study conduct

The study coordinator/local investigator, or where appropriate, a nominated designee of the sponsor, shall carry out site and study audits.

Study data

Monitoring of study data shall include confirmation of informed consent prior to inclusion; calculating and checking prior exposure to ionising radiation; data storage and data transfer procedures; local quality control checks and procedures, including QA scans, and back-up of any local databases. A nominated designee of the study team, shall carry out monitoring of study data as an ongoing activity.

Data Handling

The Principal Investigator will act as custodian for the trial data. The following guidelines will be strictly adhered to:

- Participants data will be completely anonymised
- All anonymised data will be stored in a secure location on the University's servers and on a password-protected computer these will be in line with best practice as recommended in the University of Surrey Research and Information Governance policies.
- All trial data will be stored and archived as indicated by The Medicines for Human Use (Clinical Trials) Amended Regulations 2006.
- When a subject does not meet the inclusion criteria, all questionnaires and collected data will be destroyed.

Record retention and archiving

In compliance with the ICH/GCP guidelines, regulations and in accordance with the University of Surrey Code of Research Conduct and Research Ethics, the Chief or local Principal Investigator will maintain all records and documents regarding the conduct of the study. These will be retained for at least 7 years or for longer if required. If the responsible investigator is no longer able to maintain the study records, a second person will be nominated to take over this responsibility.

Statement of confidentiality

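### The trained-versus-control comparison of levels is not protected against sex imbalance: controls have no sex quota and the ANOVA has no sex term

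*Combined protocol and SAP*

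**What the plan says.** The Synopsis (Number of participants) lists "21 trained males, 21 trained females and 21 controls(male and female", and Statistics, Sample size and justification repeats the structure as "21 females, 21 males and 21 sedentary controls, males and females". Both trained groups are single-sex and the control group is mixed. The control inclusion criteria admit either sex and give no ratio, matching or stratified recruitment.

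Sex balance is sought only among athletes. The statistics section says "In order to achieve an equal division between genders", and continues "26 males and 26 females from different indoor and outdoor sports across Team Surrey need to be recruited". (That 52 athletes do not match the 42 to be recruited is a separate point.)

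Secondary objective vii is "To ascertain whether there are any differences in the research outcomes between trained and control subjects". The outcome measures in the Synopsis include handgrip and knee-extension strength, VO2max, lean and fat mass, and bone.

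The Synopsis and the statistics section give the same analysis: group means or medians, and an ANOVA comparing pre- with post-training periods. Neither names a sex factor, a sex-stratified analysis or a defined trained-control contrast.

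**The concern.** Strength, aerobic capacity, lean mass and bone usually differ between men and women. If the male share differs between the groups compared and sex is not in the model, part of any difference in level is a sex difference. It can look like a training effect, or hide one. The plan takes care over sex balance among athletes but does not extend that care to the comparator. At stake is the interpretation of objective vii for the performance, body-composition and bone outcomes. The indoor-versus-outdoor contrast behind the sample size is not affected in this way, because controls are not part of it.

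**Working it through.** **The plan's own figures.** The Synopsis states "the study will be conducted with 18 participants in each arm" and 15% dropout. 18 x 1.15 = 20.7, rounded to 21, and 3 x 21 = 63, the stated total. (Dividing instead gives 54/0.85 = 63.5, or 64.) The arithmetic shows that the three recruitment groups are the arms being counted. It does not show how they will be compared.

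**Inputs.** Male share is 1 for trained males, 0 for trained females and 21/42 = 0.5 for trained subjects pooled. For controls it is m/21, with m not fixed by the plan. S is not in the documents; 1 to 2 within-sex SD is assumed.

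**Bias in level with no true training effect** = (male share in group A - male share in group B) x S.

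| Males among 21 controls | Pooled trained - control | Trained males - control | Trained females - control |
|---|---|---|---|
| Half (notional 10.5) | 0 | +0.50 S | -0.50 S |
| 10 | +0.02 S | +0.52 S | -0.48 S |
| 6 | +0.21 S | +0.71 S | -0.29 S |
| 15 | -0.21 S | +0.29 S | -0.71 S |
| 0 | +0.50 S | +1.00 S | 0 |

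Under 50:50 volunteering the 2.5% and 97.5% points of a binomial with n = 21 are 6 and 15 males. At 6 males the pooled bias is 0.5 - 6/21 = 0.214, so 0.21 SD at S = 1 and 0.43 SD at S = 2. For scale, the standard error of a sex-adjusted pooled contrast with 10/11 controls and no dropout is 0.267 SD (derived below). The bias is then 0.214/0.267 = 0.8 to 0.43/0.267 = 1.6 standard errors.

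**Bias in change.** The same formula applies, with S replaced by the male-female difference in mean change. A stable gap in level cancels.

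**False-positive rates** (simulation, 20,000 runs, 18 per arm, nominal 5%, no training effect; S = 0.5, 1.0, 1.5, 2.0):
- One single-sex trained group versus half-male controls: about 11%, 27%, 48% and 68-69%.
- Pooled trained versus half-male controls: 4.3%, 2.8%, 1.5% and 0.6%.
- Pooled trained versus controls with 6 of 18 male: 5.2%, 5.8%, 5.7% and 5.0%.

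The pooled test does not reject too often because the unmodelled sex difference also inflates the residual. In a half-male group the SD is sqrt(1 + S^2/4), which is 1.12 at S = 1 and 1.41 at S = 2. For the pooled contrast, leaving sex out therefore costs a shifted estimate and lost precision, rather than an inflated error rate.

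**Precision after adjustment** (residual SD = 1, no dropout).
- Additive sex term: combine the within-sex contrasts by inverse variance. For 10/11 controls: 1/(1/21 + 1/10) + 1/(1/21 + 1/11) = 6.77 + 7.22 = 13.99, so SE = 0.267. For 5/16: 1/(1/21 + 1/5) + 1/(1/21 + 1/16) = 4.04 + 9.08 = 13.12, so SE = 0.276, about 3% larger.
- Equally weighted within-sex contrasts: sqrt[(2/21 + 1/5 + 1/16)/(2/21 + 1/10 + 1/11)] = sqrt(0.3577/0.2861) = 1.12, or 12% larger.

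**Power at two-sided 0.05, for illustration.** Within one sex, 18 v 9 completers: 62% at d = 0.96 and 20% at d = 0.48. Overall, 36 v 18 (approximating a sex-adjusted analysis): 90% and 37%.

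**The case against.** The strongest defence is that the plan can be read as comparing two groups. The Synopsis eligibility text speaks of one trained group and one control group, and objective vii names trained and control subjects. Pooled trained subjects are 21:21 by design, so a half-male control group leaves no sex bias. The stated ANOVA compares the same people before and after, which removes a stable sex gap. The primary endpoint is 25(OH)D, no sex effect on it is claimed here, and the background section says controls are there to show whether young adults in general are at risk of insufficiency. All of this stands and it limits the point. It does not remove it: nothing fixes the control mix, objective vii covers all research outcomes, and no model term protects a comparison of levels.

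A reader might infer more than the documents support:
- That the plan commits to testing trained males, or trained females, against all controls. No section says so, and the 0.5 S figure applies only if that were done.
- That controls are likely to be badly split. A split of 5/16 or worse in either direction has probability of about 2.7% under 50:50 volunteering, and the documents give no evidence of uneven volunteering.
- That the bias can be measured against the 0.48 effect size in the Synopsis. That figure is for 25(OH)D in indoor versus outdoor athletes, a different outcome and contrast.
- That an uneven split costs 12% in standard error whatever the analysis. This holds only for equally weighted within-sex contrasts at 5/16; with an additive sex term it is about 3%.

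**Conclusion.** The concern holds in a limited form. Comparisons of level between trained and control subjects are open to sex confounding, because the control sex mix is left to chance and sex is absent from the model. For the pooled contrast the bias is zero with half-male controls and about 0.21 S (0.21 to 0.43 SD) at the edge of chance imbalance. It would be 0.5 S in opposite directions if each single-sex group were set against half-male controls, which the plan neither specifies nor excludes. Pre-post change is affected only if change differs by sex. These sizes rest on an assumed S of 1 to 2 within-sex SD and, for the chance range, on 50:50 volunteering. The defect concerns a secondary objective and is cheap to repair.

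**What to change.** Define the objective vii contrast as trained versus control adjusted for sex: training status, sex and time in the ANOVA, with the training-by-sex interaction as supportive. Report group means by sex, so that a mixed control mean is not set beside single-sex trained means.

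Keep 21 controls but aim for 10 to 11 per sex. This brings the pooled bias to about 0.02 S even before adjustment. The model term is the main repair. A quota alone would leave about 0.5 S in any comparison of a single-sex trained group with all controls, and it can only be set while control recruitment is open.

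The cost is one recruitment rule and a few model terms, with no added participants. Recruitment of one sex may close earlier than the other. Within-sex contrasts would rest on about 18 v 9 completers and have low power, so the sex-adjusted overall contrast should lead.

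### The dated sun-exposure rule for controls (February to October 2017) cannot contain both planned assessments in any study year and adds a screen that athletes do not have

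*Combined protocol and SAP*

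**What the plan says.** Three parts of the protocol bear on this.

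- **Calendar.** Study design: "Participants will be assessed at baseline in winter (September/October) and again at the end of the observational period in spring (March/April"). No separate timetable is given for controls. The Synopsis and the Outline of Study place them in the same 20-week before-and-after scheme as the athletes. Secondary objective ii has the same two seasons in view: "To measure vitamin D status in winter and spring".
- **Controls only.** The Control Group Inclusion Criteria require no sun beds, no sun holiday and no "returning home to a traditional sun holiday location between February 2017 and October 2017". The reason given is that "the results will be used to represent the Vitamin D status of young sporting individuals residing within the UK during these seasons". The University Athlete Inclusion criteria contain no sun-exposure item.
- **Both groups.** The Exclusion criteria, which are not limited to one group, list "Regular use of sun-beds", "Having a sun holiday one month prior to commencing the study or plans for a sun holiday within the study period", and "or will be returning home to a sun holiday location".

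The background section gives the controls an aim of their own, "to explore whether young adults are also at significant risk of Vitamin D insufficiency or deficiency", and secondary objective vii compares trained with control subjects on the research outcomes.

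**The concern.** The Synopsis names 25(OH)D as the primary endpoint, and the Hypothesis attributes low status to too little daylight and ultraviolet B. Sun exposure is therefore the protocol's own proposed determinant of its main outcome. A rule on that determinant should be the same for groups that will be compared, and its dates should match the visits. The control rule fails on both counts: it applies to one group, and its dates do not fit the stated calendar.

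The reason attached to the rule does not help. It speaks of sporting individuals, although it stands in the list for people who must not compete for the university teams, and the seasons it refers to are not those of the two visits. A recruiter cannot tell what period the rule is meant to protect, and a reader cannot tell which seasons the control results represent. At stake is the trained-versus-control comparison of 25(OH)D.

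**Working it through.** **Inputs.** Control window: 1 February to 31 October 2017, taken at its widest (Control Group Inclusion Criteria). Baseline: September/October of year Y; final assessment: March/April of year Y+1 (Study design). Interval: 20 weeks (Synopsis). The start year is not stated, so every case is shown.

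**Step 1: does any start year put both visits in the window?**

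| Start (assumed) | Baseline | Final assessment | Both inside? |
|---|---|---|---|
| Autumn 2016 | Sep/Oct 2016: outside | Mar/Apr 2017: inside | No |
| Autumn 2017 | Sep/Oct 2017: inside | Mar/Apr 2018: outside | No |
| Any other year | outside | outside | No |

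Counting 20 weeks from baseline instead of using the named months changes nothing. From 1 September 2017, 140 days leads to 19 January 2018, already past the end of the window. A 2016 baseline precedes the window whatever the interval.

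**Step 2: what do the shared exclusions already cover?** For both groups they cover a sun holiday in the month before entry or planned within the study period, returning home to a sun-holiday location, and regular sun-bed use. Months that the dated rule omits, such as November to January, are therefore still covered for sun holidays.

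**Step 3: what does the dated rule add for controls?**

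- *Autumn 2016 start.* February to April 2017 lies within the study and is already covered. The rule then runs on from 30 April to 31 October: 31 + 30 + 31 + 31 + 30 + 31 = 184 days after the latest final visit. Exposure then cannot alter a measurement already taken. The effect is mainly to exclude some controls needlessly.
- *Autumn 2017 start, read as looking forward.* February to August has passed by baseline, and September/October is covered by the shared rule. Almost nothing is added for sun holidays.
- *Autumn 2017 start, read as also covering the months before baseline.* From 1 February to a baseline on 1 September is 28 + 31 + 30 + 31 + 30 + 31 + 31 = 212 days; to 31 October it is 212 + 60 = 272 days. Controls would be screened on about 7 to 9 months of prior sun exposure, athletes on one month. An athlete with a July sun holiday and a September baseline would be eligible; a control with the same history would not.

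**Step 4: could the dates be the controls' real schedule?** The window does contain March/April 2017 and September/October 2017, but in the reverse of the stated order. The gap runs from 124 days (30 April to 1 September, 17.7 weeks) to 244 days (1 March to 31 October, 34.9 weeks), so a 20-week interval would fit. On that schedule the controls' change would run across summer and the athletes' across winter, and group would be confounded with season. Arithmetic does not rule this out, but no section says it.

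**The case against.** The strongest reply is that the rule does almost no work. The shared exclusions are tied to study entry, apply to everyone and cover the study period. The control criterion is phrased in the future for sun holidays; on that reading it adds little with a 2017 start, and with a 2016 start mostly months that no longer matter. The reference to sporting individuals suggests text carried over from athlete material, so a controls-only rule may not have been intended. The stated calendar may itself be the loose part, since it calls September/October winter.

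Most of this stands, and it limits the point. It also disposes of three stronger readings that a reader might infer:

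- *That sun holidays are uncontrolled for part of the study.* They are not; the shared exclusions cover the whole study period.
- *That athletes face no sun-exposure rule.* They do; only the dated item is additional for controls. Controls are also asked not to use sun beds while the shared rule speaks of regular use, but the text does not show whether a stricter standard is meant.
- *That the trained-versus-control comparison is biased or confounded with season.* That needs either the backward-looking reading or a separate control calendar, and the documents establish neither.

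The reply does not remove the contradiction. The dated window and the visit calendar disagree in every year, nothing reconciles them, and the rule is an operative eligibility criterion.

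**Conclusion.** The inconsistency is certain and does not depend on the missing study year: no start year places both visits inside February to October 2017. Either the dates are wrong or controls follow an unstated calendar.

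The consequence is conditional. With a 2016 start, the rule mainly turns away some controls for no purpose. With a 2017 start, and only if it covers the months before baseline, it screens controls on spring and summer exposure that athletes may have had, which could bias the trained-versus-control comparison of 25(OH)D. If the dates reflect the real control schedule, group and season cannot be separated. The size of any bias cannot be derived from the documents.

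Reach is narrow. Objective vii is secondary, the only analysis named is a pre/post ANOVA, and the indoor/outdoor athlete contrast on which the Synopsis bases its sample size is unaffected. Minor severity.

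**What to change.** 1. Delete the dated control-only criterion.
2. Apply one sun-exposure criterion to athletes and controls, anchored to each participant's own baseline and final visits. The existing shared exclusion serves, with the sun-bed wording made the same for both groups.
3. State that controls are assessed on the Study design calendar. If they are not, give their calendar and report the trained-versus-control comparison of 25(OH)D descriptively.

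The cost is protocol wording only, with no added participants, visits or assays.
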